## Section #2- Core Protocol

2.1 Objectives & Hypotheses	
Objectives:
 

1. To determine if vorapaxar safely improves arteriovenous (AV) fistula functional maturation when administered during the maturation process compared with placebo.

2. To determine if vorapaxar safely improves AV fistula patency, allowing for secondary procedures to aid in fistula maturation compared with placebo.

3. To determine if vorapaxar safely facilitates successful cannulation of AV fistulas for hemodialysis compared with placebo.

4. To determine the safety profile of vorapaxar for patients requiring hemodialysis.

 
Hypotheses:
 

1. Vorapaxar initiated two days following AV fistula creation will result in improved fistula functional maturation without increased risk of bleeding or other major adverse events.

2. Vorapaxar initiated two days following AV fistula creation will result in improved fistula patency and will increase the utility of secondary procedures to aid in fistula maturation, without increased risk of bleeding or other major adverse events.

3. Vorapaxar initiated two days following AV fistula creation will facilitate successful cannulation of AV fistulas for hemodialysis without increased risk of bleeding or other major adverse events.

2.2 Background & Rationale, Significance of Selected Topic & Preliminary Data	
Background
 
End-stage renal disease affects nearly 500,000 persons in the US and more than 2 million persons worldwide. In the US and most developed countries, hemodialysis is the predominant dialytic modality. While effective at sustaining life for most patients, hemodialysis rarely restores health. Roughly one in five patients on dialysis die each year; patients who survive experience poor functional status, impaired physical and cognitive function and severely impaired health-related quality of life. Moreover, the cost of the ESRD program exceeds \$40B in the US annually (1).
 
Hemodialysis vascular access is often referred to as the 'Achilles Heel' of dialysis care. The Brescia-Cimino (radiocephalic end-to-side) fistula is considered to be the gold standard vascular access (2); upper arm arteriovenous fistulae are often created instead. Polytetrafluoroethylene (PTFE) grafts are next best, but are frequently complicated by graft "thrombosis," commonly caused not by hematologic abnormalities, but rather by intimal hyperplasia at the venous anastomosis. Unfortunately, the majority of patients have insufficient time to undergo pre-emptive creation of an arteriovenous fistula or graft, and most patients start hemodialysis with either a temporary or "semi-permanent" tunneled catheter, often placed in one of the internal jugular veins.
 
For patients who do undergo fistula creation, either in advance of (optimally) or after starting hemodialysis, a sizeable fraction of arteriovenous fistulae never mature sufficiently to be usable for hemodialysis. It is common for patients to undergo three or more attempts at fistula creation, extending the time during which they experience a heightened risk of infection and venous stenosis/thrombosis of the internal jugular veins or in some cases other complications including superior vena cava syndrome. Therapeutic agents that could facilitate maturation of arteriovenous fistulae could

vastly improve the health and well-being of patients on hemodialysis, and could well result in enhanced survival.

#### ***Preliminary Data***

Numerous small studies have attempted to improve short- and longer-term function of arteriovenous fistulae and grafts with a variety of therapeutic agents, including warfarin, aspirin, fish oil, dipyridamole and several newer antiplatelet agents, including ticlopidine and more recently clopidogrel (3-7). In order to address the pressing need for improved outcomes, the National Institutes of Health (NIH) National Institutes of Diabetes and Digestive and Kidney Diseases (NIDDK) assembled the “Dialysis Access Consortium” more than 10 years ago – a consortium of highly qualified investigators whose aim was to design two major clinical trials to address failure of arteriovenous fistulae and grafts, respectively (8). [name] served on the Data Safety and Monitoring Board for both of the DAC trials.

The DAC investigators conducted a randomized, placebo-controlled trial of clopidogrel in patients receiving arteriovenous fistulae (9) (another trial examining arteriovenous grafts will not be discussed here). Interestingly, clopidogrel was shown to enhance short-term patency of arteriovenous fistulae, but failed to result in improved maturation, sufficient for the fistula to be consistently used for maintenance hemodialysis. Roughly six of 10 patients assigned to the trial (all at outstanding clinical centers) failed to have a usable fistula at 3-4 months, highlighting the need for more effective therapy. Despite the DAC fistula study having been stopped prematurely for “efficacy” (on the primary outcome of early fistula patency), few patients receive clopidogrel for this purpose in clinical practice.

	
3. Ability to sign informed consent 4. 3 mm venous diameter within recipient vein
 
Exclusion Criteria
 
 
1. History of stroke, transient ischemic attack or intracranial hemorrhage
 
2. History of or high level of suspicion for, severe arterial insufficiency of the hand
 
3. Indication or ongoing therapy with other antiplatelet agents, other than aspirin 81 mg daily
 
4. Indication or ongoing therapy with anticoagulants, including warfarin, low molecular weight heparin, factor Xa inhibitors or direct thrombin and other inhibitors.
 

2.4 Study Flowchart	<pre> graph LR     A[Screening] --> B[AV Fistula Creation / Randomization]     B --> C[6-week ± 2-weeks SOC Visit]     C --> D[3-month ± 2-weeks Follow-up Phone Call]     D --> E[4-month ± 2-weeks Follow-up Phone Call]     E --> F[6-month ± 4-weeks Study Visit, Ultrasound & End of Study]   </pre> 
The flowchart illustrates the study timeline. It begins with 'Screening', which leads to 'AV Fistula Creation / Randomization'. This is followed by a '6-week ± 2-weeks SOC Visit'. After the visit, there is a '3-month ± 2-weeks Follow-up Phone Call'. This is followed by another '4-month ± 2-weeks Follow-up Phone Call'. Finally, the study concludes with a '6-month ± 4-weeks Study Visit, Ultrasound & End of Study'.

2.5 Study Procedures	
Recruitment and Screening: Recruitment will be by invitation and referral from individuals' treating physicians at Stanford and SCVMC. Generally, initial screening will be performed at the time of consultation for dialysis access. Patients who appear to meet the study criteria and express interest in participation will be referred to the study team to be contacted for full screening.
 
Consent: For eligible patients informed consent will be obtained prior to the day of surgery, generally by phone and mail or in person at the preoperative visit.
 
Baseline demographics (preoperative visit, standard of care): The following data, which is collected as standard of care at the preoperative visit, will be utilized for baseline data with patient approval via the consent process:
 
 
• Age, sex, race, ethnicity, past medical history, medications, previous hemodialysis access surgery
 
• Baseline blood pressure in each arm and vascular exam
 
• Baseline vein measurements
 
 
Operative details (standard of care): The following data, which is collected during the AV Fistula Creation Procedure as standard of care, will be utilized for operative data with patient approval via the consent process:
 
 
• Location of anastomosis (lower or upper arm)
 
• Vein used (cephalic or basilic)
 
• Type of fistula (radiocephalic, brachiocephalic, brachiobasilic, other)
 


2.5 Study Procedures
	
 
• Quality of artery (normal, moderate calcification, severe calcification)
 
• Palpable thrill through completion (yes or no)
 
• Audible bruit (yes or no)
 
• BARC Bleeding Classification
 
• GUSTO Bleeding Classification
 
 
Randomization: Randomization will be performed after successful creation of an arteriovenous fistula, on the day of surgery.
 
Treatments to be compared: Half of enrolled patients will receive the study drug (vorapaxar [Zontivity™] 2.5 mg daily) and half will receive a look-alike placebo.
 
Study drug: The study drug (12-week supply of study drug or placebo) will be dispensed to enrolled patients on the day of surgery. Participants will be instructed to start taking their study medications on Day-two post-surgery.
 
6-weeks Follow-up Clinic Visit + Ultrasound (standard of care): Patients will return approximately 6 weeks after randomization to the site of their AV fistula creation procedure for a standard-of-care visit where the following data will be collected and provided to the study team:
 
 
• Patency of fistula (yes/no)
 
• Fistula being used for dialysis at least 6 times in 3 weeks (yes/no)
 
• Diameter of fistula by ultrasound
 
• Velocities of fistula by ultrasound
 
• Adverse events
 
• Additional procedures performed to aid in fistula maturation (yes/no) 
 
◦ Type of procedure
 
◦ Successful (yes/no)
 
 
 
• BARC and Gusto Bleeding Classification
 
 
3-month Follow-up Phone Call (study visit): Approximately 3 months after randomization patients will have a study phone call with a member of the research team where the following data will be collected:
 
 
• Patency of fistula (yes/no)
 
• Fistula being used for dialysis at least 6 times in 3 weeks (yes/no)
 
• Adverse events
 
• Additional procedures performed to aid in fistula maturation (yes/no) 
 
◦ Type of procedure
 
◦ Successful (yes/no)
 
 
 
• BARC and Gusto Bleeding Classification
 
 
4-month Follow-up Phone Call (study visit): Approximately 4 months after randomization patients will have a study phone call with a member of the research team where the following data will be collected:
 
 
• Patency of fistula (yes/no)
 
• Fistula being used for dialysis at least 6 times in 3 weeks (yes/no)
 
• Adverse events
 
• Additional procedures performed to aid in fistula maturation (yes/no) 
 
◦ Type of procedure
 
◦ Successful (yes/no)
 
 
 
• BARC and Gusto Bleeding Classification
 
 
6-month Follow-up Clinic Visit + Ultrasound + End of Study (study visit): Patients will have a final study visit at approximately 6 months, at Stanford University Medical Center Vascular Clinic where the following data will be collected:
 
 
• Patency of fistula (yes/no)
 
• Fistula being used for dialysis at least 6 times in 3 weeks (yes/no)
 

------------------------------------	---

	
 
• Diameter of fistula by ultrasound
 
• Velocities of fistula by ultrasound
 
• Adverse events
 
• Additional procedures performed to aid in fistula maturation (yes/no) 
 
◦ Type of procedure
 
◦ Successful (yes/no)
 
 
 
• BARC and Gusto Bleeding Classification
 
 
Participation in this study will not affect standard care of patients with AV fistulae receiving hemodialysis. The only additional treatment is administration of the study drug or placebo and additional monitoring, including one additional ultrasound, for 6 months.
 
Adverse events reporting process: The PI will review aggregated AEs each month, and AEs will be reported to the sponsor and the IRB per research guidelines. Participation for the individual will terminate if they have a serious adverse reaction that prevents future participation. In the event of adverse effects, their primary physician will be notified

2.6 Study Duration	
We estimate 24 months will be required to recruit patients with an additional six months to complete follow-up of the last enrolled subject for a total of 30 months for recruitment and final assessments.

2.7 Statistical Analysis and Sample Size Justification	
Data management and statistical coordination of the study will be performed by members of the Quantitative Sciences Unit (QSU) in the Department of Medicine at Stanford University School of Medicine and in the Data Coordinating Center in the Department of Medicine. The REDCap data management system will be used to create the data platform for storage of the clinical information.
 
Vascular Ultrasound studies will be performed at the site of surgery, either at Stanford University Hospital or SCVMC. Studies will be interpreted by the ordering vascular surgeon and reviewed by the Principal Investigator.
 
Randomization codes will be generated in block size of 4 by a statistician in the QSU.
 
Statistical analyses will be performed by MS level and PhD level statisticians in the QSU. Randomized treatment allocation will only be unblinded when all follow-up is complete, data have been cleaned and the trial statistician, Co-Investigators and Principal Investigator are in agreement.
 
Variables/Time Points of Interest
 
Primary Efficacy Outcome
 
Time to AV fistula functional maturation (defined as successful cannulation of the AV fistula for six hemodialysis sessions within three weeks).
 
Secondary Efficacy Outcomes
 
AV fistula use within 180 days of surgery.
 
AV fistula patency at 150-180 days, with at least 50% increase in vein diameter by ultrasound compared with preoperative vein diameter measurement.

AV fistula functional or anatomic maturation at 180 days as determined by the PI

### **Safety Outcomes**

Bleeding events (GUSTO and BARC Criteria)

### **BARC Bleeding Classification:**

**Type 0:** No bleeding

**Type 1:** Bleeding that is not actionable and does not cause the patient to seek unscheduled performance of studies, hospitalization, or treatment by a healthcare professional; may include episodes leading to self-discontinuation of medical therapy by the patient without consulting a healthcare professional

**Type 2:** Any overt, actionable sign of hemorrhage (e.g., more bleeding than would be expected for a clinical circumstance, including bleeding found by imaging alone) that does not fit the criteria for type 3, 4, or 5 but does meet at least one of the following criteria: (1) requiring nonsurgical, medical intervention by a healthcare professional, (2) leading to hospitalization or increased level of care, or (3) prompting evaluation

### **Type 3**

#### **Type 3a**

Overt bleeding plus hemoglobin drop of 3 to 5 g/dL\* (provided hemoglobin drop is related to bleed)

Any transfusion with overt bleeding

#### **Type 3b**

Overt bleeding plus hemoglobin drop >5 g/dL\* (provided hemoglobin drop is related to bleed)

Cardiac tamponade

Bleeding requiring surgical intervention for control (excluding dental/nasal/skin/hemorrhoid)

Bleeding requiring intravenous vasoactive agents

#### **Type 3c**

Intracranial hemorrhage (does not include micro-bleeds or hemorrhagic transformation, does include intraspinal)

Subcategories confirmed by autopsy or imaging or lumbar puncture

Intraocular bleed compromising vision

### **GUSTO Bleeding Classification**

**Severe:** Bleeding\* that was fatal, intracranial, or that caused hemodynamic compromise requiring intervention (e.g., systolic blood pressure <90 mm Hg that required blood or fluid replacement, or vasopressor/inotropic support,\*\* or surgical intervention).

**Moderate:** Bleeding\* requiring transfusion of whole blood or packed red blood cells without hemodynamic compromise (as defined above).

**Mild:** Bleeding\*: Bleeding without blood transfusion or hemodynamic compromise.

\*In all cases, bleeding must be clinically overt.

	
**Need for vasopressor/inotropic support for hemodynamic compromise, even if blood pressure
 
Statistical Methods:
 
Descriptive statistics such as means, medians, standard deviations and interquartile ranges will be presented for continuous measurements, and frequency statistics will be presented for categorical characteristics. Graphical tools such as histograms and boxplots will be used to assess distributional aspects of continuous variables.
 
Cumulative incidence plots will be derived to depict time to fistula use, stratified by treatment arm and fistula location.
 
The primary outcome is time to AV fistula maturation, defined as successful cannulation of the AV fistula for six hemodialysis sessions within three weeks.
 
Subjects who are lost to follow up or who die prior to maturation will be censored at the time of death or last recorded activity.
 
Our primary analysis will be based on the intention-to-treat principle. To that end, patients will be analyzed according to their randomized treatment assignment, and all patients randomized to treatment assignment will be included in the analysis even if they are lost to follow up or die before the end of their observation period. We will use a log-rank test stratified by location of fistula to assess whether time to maturation of AV fistula differs between treatment arms (vorapaxar versus placebo). The test will be two-sided and conducted at the 0.05 level of significance.
 
A Cox proportional hazards regression model of treatment arm and other covariates of interest will be employed secondarily to estimate an adjusted treatment effect.
 
Other secondary analyses involve the use of logistic regression techniques to evaluate the effect of treatment on secondary endpoints – use of AV fistula within 180 days and AV fistula patency within 150-180 days.
 
Power/Sample Size:
 
We have sufficient power to address our primary aim. Based upon a sample size of n=25 patients per group for this pilot study, we have approximately 70% power to detect a hazard ratio of 2.05 between treatment arms, assuming that only 50% of subjects will experience maturation by six months post randomization in the placebo group. If only 40% of subjects experience maturation by six months post randomization we have over 70% power to detect a hazard ratio of 2.15.

2.8 Specific Drug Supply Requirements	
Merck will provide the study drug and matching placebo in study kits. At conclusion of the study or upon drug expiration, the Merck GRS will be responsible for issuing a Drug Disposition Letter to the investigator for US based studies. The study investigators will be responsible for the destruction of the supplies at the study center pursuant to the ICH/GCP Guidelines, local regulations and the investigator's institutional policies. The study investigators will responsible for keeping accurate records of the clinical supplies, the amount dispensed to and returned by the patients, and the disposition at the end of the study.

2.9 Adverse Experience Reporting	
A Data Safety Monitoring Board (DSMB) comprised of one vascular surgeon, one physician with expertise about vorapaxar and one experienced in clinical trials will review unblinded data after 10 patients have completed follow-up 6-month ultrasound and after 30 patients have completed follow-up 6-month ultrasound evaluation.
 
Model study agreement will be used for reporting of adverse events.

2.10 Itemized Study Budget	
See attached.

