#### **3.4. Statistical Analysis:**

We will derive cumulative incidence plots to depict time to fistula use, stratified by treatment arm and fistula location.

The primary outcome is time to AV fistula maturation, defined as successful cannulation of the AV fistula for six hemodialysis sessions within three weeks.

Subjects who are lost to follow up or who die prior to maturation will be censored at the time of death or last recorded activity.

Our primary analysis will be based on the intention-to-treat principle. To that end, patients will be analyzed according to their randomized treatment assignment, and all patients randomized to treatment assignment will be included in the analysis even if they are lost to follow up or die before the end of their observation period. We will use a log-rank test stratified by location of fistula to assess whether time to maturation of AV fistula differs between treatment arms (vorapaxar versus placebo). The test will be two-sided and conducted at the 0.05 level of significance.

A Cox proportional hazards regression model of treatment arm and other characteristics of interest (if required) will be employed secondarily to estimate an adjusted treatment effect.

Other secondary analyses involve the use of logistic regression techniques to evaluate the effect of treatment on secondary endpoints – use of AV fistula within 180 days, AV fistula patency within 150-180 days and AV fistula functional or anatomic maturation at 180 days as determined by the PI. We will also compare rates of bleeding by treatment arm using t-tests or Wilcoxon rank sum tests as appropriate.

**UPDATED: Based on low enrollment and early termination of the study, the planned analysis as described above will not be conducted. Instead, we will conduct a descriptive analysis only.**

**UPDATED: The secondary outcome “AV fistula functional or anatomic maturation at 180 days as determined by the PI” will be defined using clinically adjudicated after a review of the medical record.**

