#### **Power/Sample Size**

We have sufficient power to address our primary aim. Based upon a sample size of n=25 patients per group for this pilot study, we have approximately 70% power to detect a hazard ratio of 2.05 between treatment arms, assuming that only 50% of subjects will experience maturation by six months post randomization in the placebo group. If only 40% of subjects experience maturation by six months post randomization we have over 70% power to detect a hazard ratio of 2.15.

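### The stated power of about 70% (HR 2.05) and over 70% (HR 2.15) does not follow from the planned design, which gives about 52% and 51%

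*Protocol*

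**What the plan says.** The power paragraph is the same in Protocol section 2.7 and in the SAP (Power/Sample Size). It opens with "We have sufficient power to address our primary aim". For 25 patients per group it then makes two claims:

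- Scenario 1: "we have approximately 70% power to detect a hazard ratio of 2.05 between treatment arms". The placebo maturation rate behind this claim is 50% at six months.
- Scenario 2: "If only 40% of subjects experience maturation by six months post randomization we have over 70% power to detect a hazard ratio of 2.15". This sentence does not name the arm. It follows directly on one about the placebo group and is read that way here.

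The primary test, in both documents, is a two-sided 0.05 log-rank test stratified by fistula location. No formula, event count, follow-up time or dropout allowance accompanies the power figures.

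On follow-up, the Protocol's flowchart (section 2.4) ends with "6-month ± 4-weeks Study Visit, Ultrasound" and end of study. Section 2.5 says "Patients will have a final study visit at approximately 6 months". Section 2.6 says "We estimate 24 months will be required to recruit patients with an additional six months to complete follow-up of the last enrolled subject".

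SAP section 3.4 carries a later update: "Based on low enrollment and early termination of the study, the planned analysis as described above will not be conducted". A descriptive analysis takes its place. The power section has no such update.

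**The concern.** The power of a log-rank test depends on the number of events. Here the event is maturation, and the plan itself assumes that only 50% or 40% of placebo patients reach it by the time follow-up ends. With 50 patients that leaves far fewer than 50 events, and a hazard ratio near 2 then needs more events than the trial could supply for 70% power.

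The stakes are limited. No test will be run, so no decision now rests on the figure. But the uncorrected text tells a reader that full enrollment would have given about 70% power, so that low enrollment alone cost the trial its chance. At the stated effects, full enrollment would have given roughly even odds. Protocol section 2.12 commits to a manuscript on design and results, which could carry the figure forward, and anyone sizing a later trial from it would plan too few patients.

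**Working it through.** **Inputs.** From Protocol 2.7 and the SAP power section: n = 25 per arm; placebo maturation by six months p0 = 0.50 with HR 2.05, or p0 = 0.40 with HR 2.15; two-sided alpha 0.05. From Protocol 2.4 and 2.5: follow-up ends at about six months. Assumed: proportional hazards and no dropout.

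**Trying to reproduce the plan's figures.** No standard calculation that keeps the stated maturation rates and six-month follow-up reaches 70%. Counting all 50 patients as events does fit both statements:

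- HR 2.05: Φ(√50 × 0.7178/2 − 1.96) = Φ(0.578) = 71.8%
- HR 2.15: Φ(√50 × 0.7655/2 − 1.96) = Φ(0.746) = 77.2%

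That would contradict the 50% and 40% assumptions. Whether it is the source is only an inference, since the documents show no formula.

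**Power under the written design.**

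1. Vorapaxar maturation by six months, p1 = 1 − (1 − p0)^HR:
   - 1 − 0.5^2.05 = 0.7585
   - 1 − 0.6^2.15 = 0.6666
2. Expected events, d = 25 × (p0 + p1):
   - 25 × 1.2585 = 31.5
   - 25 × 1.0666 = 26.7
3. Schoenfeld power, Φ(√d × ln(HR)/2 − 1.96):
   - Φ(2.013 − 1.96) = 52.1%
   - Φ(1.976 − 1.96) = 50.7%
4. Freedman power, Φ(√d × (HR − 1)/(HR + 1) − 1.96):
   - Φ(1.931 − 1.96) = 48.8%
   - Φ(1.885 − 1.96) = 47.0%
5. Log-rank simulation, 20,000 runs per scenario: unstratified 51% to 52% and 49% to 50%; stratified with two equal strata 51.0% and 48.0%. Weibull shapes 0.6, 1 and 2 give 51.9%, 51.4%, 51.9% and 50.1%, 49.4%, 50.4%, so the six-month result does not need a constant hazard.

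**What 70% would take.** Events = 4 × (1.96 + 0.524)² / ln(HR)² = 47.9 and 42.1. As an outer bound, if every vorapaxar patient matured by six months, the stated placebo rates would still allow only 25 × 0.5 + 25 = 37.5 and 25 × 0.4 + 25 = 35 events. With 25 per arm, 70% power needs an HR of about 2.38 or 2.55. At the stated HRs it needs 48/1.2585 = 38.1 and 43/1.0666 = 40.3 patients per arm, that is 39 and 41.

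**Other readings.**

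| Reading | HR 2.05 | HR 2.15 |
|---|---|---|
| Stated by the plan | about 70% | over 70% |
| Six months, Schoenfeld | 52.1% | 50.7% |
| Constant hazard to month 7 (end of the +4-week window; 34.1 and 29.3 events) | 55.4% | 54.4% |
| One-sided 0.05 (contradicts the plan) | 64.4% | 63.0% |
| Common close at month 30, uniform accrual, constant hazard (44.7 and 41.7 events) | 67.0% | 69.6% |
| 40% read as the rate over both arms (20 events) | not applicable | 40.2% |

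**The case against.** The best defence is that the power calculation may have assumed follow-up to a common closing date. The paragraph gives the six-month figure as a maturation rate and does not say what follow-up the power rests on, and Protocol section 2.6 describes 24 months of recruitment plus six. Following everyone to month 30 gives 67.0% and 69.6% by Schoenfeld with uniform accrual. If 60% of patients enrolled in the first 12 months, it gives 67.7% and 70.5%, which fits both statements. So whether this route reaches 70% in the second scenario depends on an accrual pattern that the Protocol does not give. It also depends on the formula: with uniform accrual, Freedman gives 63.4% and 65.5%, and simulation about 65% to 66% and 67% to 68%.

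This may explain where the figures came from, but it does not rescue them. Protocol sections 2.4 and 2.5 close each patient's study at about six months, and section 2.6 adds six months only so that the last patient can finish.

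Three smaller points stand in part:

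- The all-mature ceiling is a bound on events, not a scenario consistent with the hazard ratios being tested.
- Stratification moves simulated power by only a point or so, and the 1 to 2 non-completers expected in SAP section 3.2 could only lower it. A corrected statement should name its formula and assumptions.
- With the test withdrawn, the practical effect is small. That limits the severity but leaves the figure wrong.

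**Conclusion.** The concern holds, as a minor one. Under the written design the power is about 52% for HR 2.05 and 51% for HR 2.15, or roughly 50% by any of the two-sided methods tried (47% to 52%). That is some 18 to 20 points below the stated figures, and too wide a gap to come from rounding or choice of formula. The result rests on proportional hazards, no dropout, follow-up ending at six months, and the 40% being the placebo rate. Censoring for death or loss would lower power further, and using the whole final-visit window adds only about three to four points. Confidence in the arithmetic is high. What remains unknown is how the plan's figures were obtained.

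**What to change.** Add a dated update to the SAP power section, in the style already used in section 3.4, along these lines:

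> The planned 50 patients (25 per arm), each followed for six months, would have given about 31 (or 27) events and about 52% (or 51%) power for a hazard ratio of 2.05 (or 2.15). Hazard ratios of about 2.4 (or 2.55) would have been detectable with 70% power. These figures use Schoenfeld's formula for a two-sided 0.05 log-rank test and assume proportional hazards and no dropout, with no allowance for stratification.

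The note should also state which arm the 40% refers to, withdraw the sentence claiming sufficient power, and refer to the update in SAP section 3.4 that cancels the test. Use the corrected figures wherever Protocol section 2.7 is cited or reported, including the planned manuscript. The Protocol text can stay as the record of what was planned.

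The cost is wording only: no extra patients and no change to the descriptive analysis. The stated planning power becomes less favourable.
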